Aim 1. We will use a linear GEE regression model with main effects for the intervention (standard risk and prevention plus genetic education versus standard risk and prevention education only), time, and the interaction terms between the intervention and time. The interaction term will be the main test of interest as it assesses average departure from the slope due to the intervention. We will include other covariates related to dropout or involving potential baseline imbalances between the intervention groups as appropriate, as well as month of completion of the questionnaires to account for seasonality.

We will perform analyses to test whether participants and eligible non-participants differ on basic demographic variables using cross-sectional logistic or linear regression models for binary or continuous factors, respectively. We will perform attrition analyses to determine whether participants and dropouts differ on key variables. We will include these factors in the above ITT model to see if they affect the results. A few randomly missing observations have only a slight impact on power and do not introduce bias. However, large numbers of non-randomly missing values can bias results.

We also will conduct mediator analyses to determine whether the effect of the intervention on prevention behaviors is explained by health beliefs or cancer distress. We will use a series of models to examine whether (a) the intervention is predictive of the mediator, (b) the mediator is predictive of prevention behaviors in a multivariable model controlling for the intervention, and (c) the addition of the mediator to a

multipredictor model for prevention behaviors attenuates the estimated coefficient for the intervention. To assess mediation effects, we will use the approaches by Imai et al., which are available through add-on packages to existing statistical software (such as R and STATA) (Imai et al. 2010, Imai et al. 2012). Similar to the method of Preacher and Hayes (Preacher et al. 2008), their methods employ bootstrapping to estimate mediating causal effects . These analyses will be used to estimate the direct effect of the intervention via pathways other than through the posited mediator, its indirect effect via the mediator, and the degree of mediation. This approach will allow us to quantify the effect of the intervention due to the potential mediator (if any), which can inform future interventions or prevention strategies.

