Aim 2. Hypothesis testing for the binary outcome of full-body examination (yes/no) will follow the general analytic outline used in Specific Aim 1. This outcome will be modeled using the logistic framework of the GEE approach (i.e. specifying a logit link function), which properly accounts for the induced correlation from the repeated measures on participants over time, to assess ITT differences. These ITT differences comparing the probability of skin examinations will be presented as odds ratios with corresponding 95% confidence intervals where models will include main effects for intervention (standard risk and prevention plus genetic education versus standard risk and prevention education only), time (0, 6, and 12 months), and interaction term between the intervention and time. The interaction term will be used to test for possible differences in effects over time in the two study arms as the main test of interest. In addition, the logistic GEE model will contain baseline covariates and variables related to study participation and/or attrition as appropriate.

Exploratory Aim 3. We will use the GEE Poisson or ordinal regression models as appropriate with main effects for the intervention, time, and interaction term between the intervention and time, and will adjust for date of study enrollment to account for seasonality. Specifically, we are interested in estimating the intervention's efficacy in reducing the average number of red or painful sunburns in children.

All statistical analyses will be conducted by a member of the Biostatistics Core under the direction supervision of [name].

Analyses among individuals with low-risk *MC1R* genotypes will be conducted in a similar fashion to those detailed above. Because we do not expect to see ITT differences in prevention behaviors comparing those who receive a risk and prevention education intervention that includes feedback of *MC1R* genotype to those who receive a risk and prevention education session that includes only standard information among the low-risk group, power analyses are omitted.

Pilot study Aim 1. The overall prevalence of *MC1R* genotypes will be calculated with corresponding 95% confidence intervals.

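### Aim 1: with complete data, baseline covariates entered as main effects cannot alter the arm-by-time test, so the planned adjustment for baseline imbalance does not reach the primary analysis

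*Combined protocol and SAP*

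**What the plan says.** STATISTICS, Aim 1, specifies a "linear GEE regression model with main effects for the intervention", with time and intervention by time as the remaining terms. On the test it says "The interaction term will be the main test of interest as it assesses average departure from the slope due to the intervention".

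On adjustment it says "We will include other covariates related to dropout or involving potential baseline imbalances between the intervention groups as appropriate". The one covariate it names outright is survey month: "as well as month of completion of the questionnaires to account for seasonality". The next paragraph adds "We will perform attrition analyses to determine whether participants and dropouts differ on key variables" and, on what is done with the result, "We will include these factors in the above ITT model to see if they affect the results".

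Aim 2 "will follow the general analytic outline used in Specific Aim 1" and gives its visits as "time (0, 6, and 12 months". I therefore take baseline to be an outcome row in Aim 1 too, although the Aim 1 text does not say so.

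The plan gives no list of covariates (month apart), no rule for choosing them, no statement of whether they enter as main effects or with time, and no working correlation.

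**The concern.** The adjustment is meant to protect the primary comparison against chance imbalance. The primary comparison is a difference in change over time, whereas a main effect of a time-constant covariate shifts a person's level equally at every visit. If the form is as it appears, the adjustment acts on a part of the model that is not tested. An imbalanced covariate that predicts change would be left uncorrected while the report could state that imbalance had been adjusted for. The baseline hours report, which is already collected, is used only as the start of a slope and not as a covariate, which costs precision. The covariate set is also left open until imbalance and dropout have been seen.

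**Working it through.** **Inputs.** From Study power, Aim 1 (white, non-Hispanic): 250 per arm, two-sided alpha 0.05, 80% power, correlation 0.1, 20% attrition, SD 1, 3 and 5, detectable differences 0.17, 0.50 and 0.84 hours. I read the SD as the between-person SD of hours and code the visits 0, 1, 2. z(0.975) + z(0.80) = 2.8016.

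**1. The plan's own figure.** For a slope difference with equal correlation, detectable difference = 2.8016 × SD × sqrt(2(1 − rho)/(n × Sxx)), with Sxx = 2.
- n = 250: 2.8016 × sqrt(0.9/250) = 0.168 SD, giving 0.168, 0.504 and 0.841 hours. These match the printed values.
- n = 200 (20% lost): 0.188, 0.564 and 0.940 hours.

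The printed figures agree with the slope test, but only with no loss for attrition. The plan gives no formula, so this is a mismatch of unknown cause and a separate matter.

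**2. Complete data.** With three equally spaced visits, the estimated slope difference is the arm difference in the mean of (Y12 − Y0)/2. A covariate that is constant within a person, with one coefficient for all visits, contributes equally to Y0 and Y12 and drops out. A simulated Aim 1 GEE (SD 3, rho 0.1, exchangeable) gave 0.1427, SE 0.1868, both before and after adding the covariate. The same held under an independence working correlation and at rho 0.5. With month terms also in the model the estimate moved by about 0.003 hours on average.

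**3. Where the form matters.** Further simulations used 250 per arm, SD 3, rho 0.1 and no true effect. I assumed a covariate worth 1.0 hour per SD and an arm imbalance of 0.3 SD.

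| Scenario | No covariate | Main effect | Covariate × time |
|---|---|---|---|
| Complete data, covariate also alters slope by 0.5 h per SD per interval: bias | 0.14 | 0.14 | −0.01 |
| same: false-positive rate | 13.0% | 13.0% | 4.8% |
| About 20% dropout, same dependence in both arms: bias (independence) | −0.016 | −0.005 | −0.004 |
| About 22% dropout, opposite dependence by arm: bias (independence / exchangeable) | −0.15 / −0.11 | 0.006 / 0.006 | 0.006 / 0.006 |
| same: false-positive rate | 12.0% / 8.1% | 4.6% / 4.1% | 4.8% / 4.3% |

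The first row is close to its expected value, 0.3 × 0.5 = 0.15.

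**4. Imbalance in baseline hours.** If the arms differ by d at baseline by chance, the expected follow-up difference is rho × d. The expected slope shift is (rho × d − d)/2 = −(1 − rho)d/2 = −0.45d per interval at rho 0.1. A main-effect covariate does not address this.

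**5. The alternative.** Take the mean of the two follow-up reports adjusted for baseline hours, with 200 per arm and ignoring the small cost of estimating the baseline coefficient. Residual variance = (1 + rho)/2 − rho².
- rho 0.1: 0.55 − 0.01 = 0.54; detectable difference 2.8016 × sqrt(2 × 0.54/200) = 0.206 SD.
- Slope test, effect sustained at both visits (0, Δ, Δ): slope = Δ/2, so Δ = 2 × 0.188 = 0.376 SD.
- rho 0.5: adjusted follow-up 2.8016 × sqrt(2 × 0.50/200) = 0.198 SD; slope test 2 × 2.8016 × sqrt(0.5/200) = 0.280 SD.
- Effect growing linearly by b per visit, rho 0.1: the follow-up mean is 1.5b, so b = 0.206/1.5 = 0.137 SD, against 0.188 SD for the slope test.

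At SD 3 the sustained effect is 0.376 × 3 = 1.13 hours against 0.206 × 3 = 0.62 hours.

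**The case against.** **Attrition.** The plan expects 20% loss and its sentence also covers covariates related to dropout. A reader might infer that the adjustment does nothing at all. The documents do not support that: with visits missing, main effects can move the tested term, and under arm-dependent dropout they removed the bias. For the same reason one should not infer that the check on attrition factors must come back negative. It follows directly on the attrition analyses and so operates when data are incomplete. It already reads much like a sensitivity analysis.

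**Little to correct.** If a covariate affects level only, comparing change already removes its imbalance. Large imbalance is also rare: with 250 per arm, a 0.3 SD difference in a given covariate has two-sided probability of about 0.08%, and 0.2 SD about 2.5%. Averaged over randomizations the error rate stays near nominal. This stands, so the 13.0% above describes an unlucky trial, not the design.

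**Data-driven choice.** A reader might infer serious type I error inflation. Where covariates cancel, choosing them cannot affect the test. With about 20% dropout, taking the best of unadjusted, imbalance-triggered and fully adjusted main-effect models gave 5.5%, against 4.7 to 4.8% for each alone. Allowing a covariate-by-time model among the choices gave 6.9%, against 5.0 to 5.7%. The gain from fixing the list is real but modest.

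**Form and month.** The plan never states main effects only; that is a reading. Month is fixed in advance. A common month effect does sit awkwardly with a 12-month recall at baseline and a 6-month recall at follow-up, but its importance depends on assumed seasonality, and the Hispanic/Latino visits at 3 and 9 months behave differently. I treat it as secondary.

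**The remedy changes the contrast.** It does: a baseline-adjusted follow-up difference is not a slope difference. But the stated objective is lower exposure at both short-term and long-term follow-up, which the follow-up contrast addresses directly.

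**Conclusion.** The point holds in limited form. On the natural reading, the Aim 1 adjustment for baseline imbalance has no effect on the primary test when all visits are observed. Under the planned attrition it has some effect, usually slight. Imbalance in baseline hours, or in a covariate that predicts change, stays uncorrected.

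The practical loss is mainly precision: about 0.38 against 0.21 SD for a sustained effect at correlation 0.1 and 200 per arm, narrowing to 0.28 against 0.20 SD at correlation 0.5. The adjusted follow-up analysis is also better for a linearly growing effect at correlation 0.1.

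This rests on equal correlation across visits, equal SD, visits at 0, 6 and 12 months, and baseline as an outcome row. Covariate effects, imbalances and dropout patterns in the simulations are assumed; the documents give none. Exact cancellation applies to the identity link of Aim 1. It was not examined for the logit model of Aim 2, where only the open covariate choice carries over.

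**What to change.** Make the primary Aim 1 analysis a GEE of follow-up hours (6 and 12 months; 3 and 9 months for the Hispanic/Latino population). Regress on arm, visit, baseline hours, month of the follow-up survey and a short covariate list fixed before unblinding, for example age, sex and tanning response. Test the arm contrast.

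If the three-visit model is kept, enter the fixed covariates as covariate by time. In either case, do not select covariates on observed imbalance, and label any model with added dropout predictors as a sensitivity analysis.

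The cost is SAP wording and a few model terms, since every variable is already collected. The one real downside is that the declared primary contrast changes from a slope difference to a baseline-adjusted follow-up difference. That must be restated, and the power statement recalculated to match.

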Follow-up assessments. To capture changes in early detection and prevention items over time, we will re-administer the 14-item measure for adults and 12-item measure for adults reporting for children at 6 and 12 months for our white, non-Hispanic population and at 3 and 9 month for our H/L population. A 12 month follow-up assures that all white, non-Hispanic participants are under observation for a full year, thus implicitly allowing all participants to experience both winter and summer months during which preventive behaviors may differ. We also will ask all participants to complete instruments assessing potential mediators at both follow-up times. The questionnaires used at follow-up will be e-mailed to participants as links to a web-based interface and/or mailed along with prepaid return envelopes.

Participant retention. To enhance retention at the 6 and 12 month time points for our white, non-Hispanic population and at 3 and 9 month for our H/L population, patients randomized to either the intervention or placebo arm will receive a series of two gift cards, each in the amount of \$20. The first will be mailed to participants along with the summary letter after the health education session. The second will be sent via U.S. mail after completion of the 12 month follow-up questionnaire for our white, non-Hispanic participants and after completion of the 9 month follow-up questionnaire for our H/L participants. Consented patients with low risk *MC1R* genotypes who are not selected for randomization will receive one \$10 gift card to be included in the mailing that conveys their ineligibility for further study participation.

We also will supplement monetary incentives for questionnaire completion with reminder post cards mailed the month preceding study assessments and birthday cards, which we have used in previous studies involving recruitment and retention of individuals at increased genetic risk for cancer in which telephone and in-person genetic counseling, disclosing test results, and periodic follow up assessments were undertaken for study participants (Pal et al. 2011, Christie et al. 2012, [name] et al. 2012). All communications will include postage paid response cards to update contact information. We conservatively estimate study attrition over the follow-up period at 20%.

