For Exploratory Aim 3, the 12-item measure for children age 10 years or younger as reported by the study participant (Section B) will be used. Study participants with at least one child 10 years of age or younger will complete Section B, and those participants with more than one child within this age range are instructed to answer questions in this section thinking about the oldest child. Section B elicits responses about sun protection behaviors of the child, including number of red or painful sunburns over the past year for white, non-Hispanics and over the past 9 months for our H/L populations.

Since intermittent sunburns in adolescence are strongly associated with future melanoma risk (Armstrong et al. 1993, Gandini et al. 2005), the outcome of particular interest for our exploratory aim is the number of red or painful sunburns that lasted a day or more over the past timeframe. This outcome is measured by Section B, Q5, with a range of possible responses of 0 through 5 times (5 indicating 5 or more red or painful burns). We will tailor the timeframe to correspond to the baseline, 6 or 12 month survey for white, non-Hispanic participants and at baseline, 3 or 9 months survey for H/L participants).

STATISTICS

There will be no merging of data between the white non-Hispanic study population and

the H/L study population data. We will conduct mutually exclusive analyses within each of these two study populations.

Non-Hispanic study population

For our white, non-Hispanic population, the number of participants, 500 with high risk *MC1R* genotypes required to participate in this study was based upon the power calculations below.

Study power, Aim 1. We determined that randomizing 500 participants with high risk *MC1R* variants (250 each to the intervention and placebo arm) ensures 80% power to detect mean differences in hours of sun exposure of 0.17, 0.50 and 0.84, respectively, when the estimated standard deviation of the observed means is equal to 1, 3 and 5, respectively, when comparing participants with high risk genotypes who are randomized to intervention to participants with high risk genotypes who are randomized to placebo. These calculations are based on two-sided, alpha=0.05 level tests assuming a conservative auto-correlation equal to 0.1 to account for the repeated measures of participants over time, and a conservative 20% study attrition.

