Study power, Aim 2. We estimate a 20% incidence of having a skin examination with the past 9 months among control participants, with a range of 15% to 35%, and estimate study attrition of 20%. Using these estimates, we determined that randomizing 400 participants with high-risk *MC1R* variants (200 per study arm) ensures 80% power to detect an odds ratio of at least 1.95 to 1.73 when comparing participants with high-risk genotypes randomized to intervention versus those randomized to control for the skin examination (yes/no) outcome.

General approach. All analyses will be done within SAS, version 9 or later, primarily using PROC UNIVARIATE, FREQ and GENMOD. In the primary analyses, we will use an intention-to-treat (ITT) approach in which participants are analyzed in their randomized conditions regardless of the number of interventions or number of follow-up assessments they complete. Two-sided tests will be used for all hypotheses. We will assess the data for missing and out-of-range values with basic statistical procedures, including univariate statistics and graphs (histograms, box and whisker plots, scatter plots, and Q-Q plots). We will investigate data quality and integrity before any statistical modeling to ensure unbiased estimation.

The primary aim of this proposal is to test for significant ITT differences in the proportion of study subjects participating in skin prevention behaviors over the 12-month follow-up period by comparing those who receive a risk and prevention education intervention that includes feedback of *MC1R* genotype to those who receive a risk and prevention education session that includes only standard information. Our two primary outcomes of interests are (1) the average hours per week (weekdays and weekend) spent outside between 10am – 4pm; and (2) the completion of a full body skin examination for skin cancer (yes/no) by self, partner or clinician.

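### The GEE analyses of both primary outcomes name no working correlation and no method for dropout that depends on earlier follow-up outcomes; if that dropout differs by arm, the effect can be biased

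*Combined protocol and SAP*

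**What the plan says.** In the combined protocol and SAP, STATISTICS, Aim 1: "We will use a linear GEE regression model with main effects for the intervention", time and their interaction, and "The interaction term will be the main test of interest as it assesses average departure from the slope due to the intervention". Aim 2 follows the same outline: "This outcome will be modeled using the logistic framework of the GEE approach (i.e. specifying a logit link function"), with "time (0, 6, and 12 months") in the model, so baseline and first follow-up are responses and not covariates. General approach states intention-to-treat whatever number of assessments is completed, in SAS "primarily using PROC UNIVARIATE, FREQ and GENMOD". Under Participant retention: "We conservatively estimate study attrition over the follow-up period at 20" per cent.

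On missing data, Aim 1 plans to compare dropouts with those who stay, to add dropout-related covariates where suitable, and to refit the model with the factors found. Aim 2 adds attrition-related variables on the same terms. Aim 1 then says "A few randomly missing observations have only a slight impact on power and do not introduce bias", and follows this with a warning about large amounts of non-random missingness. Neither aim states a working correlation, weights, imputation or a likelihood-based model. A correlation appears only in the Aim 1 power paragraph for the white, non-Hispanic population: "two-sided, alpha=0.05 level tests assuming a conservative auto-correlation equal to 0.1".

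**The concern.** Unweighted GEE uses the visits that were observed. Covariates in the outcome model deal with dropout that those covariates explain. They do not deal with dropout after the first follow-up that depends on what the participant reported there. That outcome is a response in the model, so it cannot also be an adjustment covariate. Follow-up distress is a named mediator, so adjusting for it would remove part of the effect under test.

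Dropout that differs by arm is plausible in this design. Only the intervention arm receives genotype results during follow-up; the placebo arm receives them at the end. The RISKS section expects possible stress and worry from this feedback, and staff will contact participants whose distress rises sharply. If staying in the study depends on behaviour or distress differently in the two arms, the arm-by-time term, which is the main test for both outcomes, mixes the intervention effect with selective loss. The bias can go either way.

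**Working it through.** **Inputs from the documents.** 250 high-risk participants per arm; two-sided alpha 0.05; correlation 0.1; 20% attrition; Aim 2 control rate 20% and odds ratio 1.8.

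**Assumed, not in the documents.** The strength and direction of outcome-dependent dropout, and within-person correlations above 0.1.

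**The plan's own figure.** Detectable difference = (1.960 + 0.842) × SD × √(2f/n).
- Mean of three visits: f = (1 + 2×0.1)/3 = 0.40, n = 225 (average of 250, 225 and 200). Result for SD 1, 3, 5: 0.167, 0.501, 0.835.
- Slope per 6-month step: f = (1 - 0.1)/2 = 0.45, n = 250. Result: 0.168, 0.504, 0.840.

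Both agree with the stated 0.17, 0.50 and 0.84 to within rounding. So 0.168 SD per step is a fair yardstick for the slope test.

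**Hours: 12-month contrast, independence working correlation.** With time as categories, the estimate is the difference in observed cell means. Let 20% leave after 6 months with P(drop) = expit(c + 0.8z), where z is standardised 6-month hours. A 20% loss gives c = -1.562. The mean of z among those who stay is E[z(1 - P(drop))]/0.8 = -0.145. With correlation ρ between 6 and 12 months, the observed 12-month mean in that arm shifts by -0.145ρ:
- ρ = 0.1: -0.30 - 0.0145 = -0.31
- ρ = 0.5: -0.30 - 0.073 = -0.37
- ρ = 0.7: -0.30 - 0.102 = -0.40

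Large simulations (400,000 to 1,000,000 per arm) agree and add the other cases:

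| Case (true effect -0.30 SD) | ρ = 0.1 | ρ = 0.5 | ρ = 0.7 |
|---|---|---|---|
| Intervention arm only, independence | -0.31 | -0.37 | -0.40 |
| Opposite directions by arm, independence | -0.33 | -0.45 | -0.50 |
| Intervention arm only, exchangeable, data exchangeable | -0.304 | -0.295 | -0.299 |
| Intervention arm only, exchangeable, data AR(1) | -0.304 | -0.310 | -0.307 |

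With the same rule in both arms, estimates were -0.297 to -0.305 in every setting. If low-hours participants are the ones who leave the intervention arm, the sign of the shift reverses: -0.30 + 0.073 = -0.23 at ρ = 0.5.

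**Hours: slope test.** 1,500 trials of 250 per arm, true effect zero, dropout odds doubling per SD of the previous outcome, 20% lost per arm, independence.
- Intervention arm only: bias -0.008, -0.036 and -0.049 SD per step at ρ = 0.1, 0.5 and 0.7; type I error 0.06, 0.11 and 0.23.
- Opposite directions: bias -0.014, -0.069 and -0.098; type I error 0.05, 0.29 and 0.64.
- Same rule in both arms: bias about zero, type I error 0.05.

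Against 0.168, the one-arm bias at ρ = 0.1 is 0.008/0.168 = 5%, and at ρ = 0.5 it is 0.036/0.168 = 21%. Weights estimated from arm, previous outcome and their product cut the bias to at most 0.002 and gave type I error of 0.027 to 0.057.

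**Skin examination: 12-month odds ratio, independence.** The true intervention rate is 0.25×1.8/(1 + 0.25×1.8) = 0.310. At correlation 0.5, P(exam at 12 | exam at 6) = 0.310 + 0.5×0.690 = 0.655, and P(exam at 12 | none at 6) = 0.310 - 0.5×0.310 = 0.155. Let non-examiners in the intervention arm have three times the dropout odds, with 20% lost after 6 months. Dropout is then 0.246 without and 0.098 with a 6-month examination. The observed rate is (0.310×0.902×0.655 + 0.690×0.754×0.155)/0.8 = 0.330, and the odds ratio is (0.330/0.670)/0.25 = 1.97. Over correlations 0.1 to 0.5 and losses of 10.6% to 20% in that interval, the range is 1.82 to 1.97. It is 1.80 to 1.81 with the same rule in both arms and 1.84 to 2.25 with opposite rules.

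**The case against.** A reader might infer that GEE is valid here only if dropout is unrelated to earlier outcomes. The documents and the working do not support that. For hours, a linear GEE whose working correlation fits is nearly unbiased under the same dropout, and exchangeable fitted to AR(1) data was off by no more than about 0.01 SD. If both arms share the dropout rule, the interaction is essentially unbiased even under independence. Nothing in the documents shows that dropout will differ by arm, and independence is not stated.

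At 0.1, the only correlation given, the bias is small. The plan also has real protections: attrition analyses, a refit with dropout factors, incentives, reminders, and an attrition figure it calls conservative. For Aim 2, eligibility makes the baseline examination almost constant, so only the first follow-up examination can drive this kind of dropout.

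All of that stands, and it limits the size of the point. It does not remove it. The protection for hours depends on a working correlation that the plan never commits to. The Aim 2 remark that GEE accounts for correlation over time does not choose one. For the slope test, lower correlation means larger variance, so calling 0.1 conservative implies that a higher value is expected. The planned covariates do not reach dropout driven by the first follow-up outcome.

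**Conclusion.** The point holds as a conditional one. The plan leaves both primary analyses open to bias when three things coincide: dropout depends on earlier follow-up outcomes or distress, that dependence differs by arm, and the working correlation is independence or fits poorly. Under the one-arm assumptions above, the 12-month hours effect is overstated by 0.0145/0.30 = 5% at correlation 0.1, 0.073/0.30 = 24% at 0.5 and 0.102/0.30 = 34% at 0.7. The examination odds ratio moves from 1.8 to between 1.82 and 1.97. The dropout strengths and the correlations above 0.1 are assumptions, so these are illustrations and not forecasts.

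It would go too far to read the larger figures as the expected bias, or to call the quoted missing-data sentence an error: it concerns a few randomly missing values and is correct as written. The weakness is that the plan names the risk of non-random loss and then offers no method for the part of it that the first follow-up outcome could explain. This should be changed, because the remedy is cheap and uses data already planned for collection.

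**What to change.** For hours, make the primary analysis a likelihood-based repeated-measures model with unstructured covariance and the same arm-by-time terms. A linear GEE with a pre-specified working correlation other than independence gives nearly the same protection.

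For skin examination, use inverse-probability-weighted GEE, or multiple imputation followed by GEE. The dropout or imputation model should contain arm, earlier-visit outcomes, distress and their interactions with arm. Distress then informs the dropout model without entering the outcome model.

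State the working correlation for every GEE, and keep the unweighted GEE as a sensitivity analysis. Apply this to both study populations, at 6 and 12 months and at 3 and 9 months. These methods still assume that dropout is explained by observed data.

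The cost is SAP wording, modest programming and slightly wider intervals. In the slope simulations for hours at correlation 0.1 with the same dropout rule in both arms, power for 0.168 SD per step was 0.738 weighted and 0.736 unweighted.
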